- Social functioning is an important contributor to disability in those with depression and chronic pain. We will measure social isolation using PROMIS measures, based on our preliminary data, by older Veterans with cLBP;
- Current medications (regularly scheduled and as-needed) will be collected at baseline and subsequent assessments from CPRS and then confirmed with the subject over the telephone. Subjects are also asked if they are taking additional medications. As described, we will create four “yes/no” variables reflecting medication use: acetaminophen, non-steroidal anti-inflammatory drugs (NSAIDs), opioids (including tramadol), and other agents such as anti-depressants used specifically for pain (versus depression), gabapentin, other anticonvulsants, corticosteroids, topical anesthetic

and capsaicin preparations.

- Variables abstracted from the electronic medical record include (baseline, 3, 6): opioid use, psychotropic medications, hospitalizations, and clinic visits (including mental health appointments). These are important health utilization outcomes that will be explored in future studies.

Proximal/Behavioral Outcomes

- Physical activity: We will evaluate overall physical activity level using a portable, lightweight, Omron HJ-320 pedometer. Participants will wear the pedometer clipped to their right lateral waistband for 24 hours per day for 7 consecutive days (except during shower or water activities) to obtain 5 complete days of physical activity data. This will be explained in detail at the time of recruitment call. More details about the device are provided in a separate attachment. Instructions to Veterans on how to safely enhance physical activity using this device are also provided in a separate attachment.

Other measures associated with achieving behavioral and clinical outcomes

- Patient Activation Measure (PAM) assesses patients' skill, confidence, and knowledge in managing issues related to their healthcare.
- Arthritis Self-efficacy scale is a 10-point Likert scale that measures the belief or confidence the subject has to perform 8 specific activities or tasks, based on arthritis.
- Physical activity contemplation ladder;
- Expectations of the intervention are asked with the following three questions: 1) How likely is this program to improve my ability to walk? 2) How likely is this program to improve my back pain? 3) How likely is this program to improve my depression/mood?

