Our formative evaluation may help to identify parts of the process that need refinement to maximize the feasibility and extension of the project to different sites (in anticipation of the IIR proposals). Also, part of the formative evaluation process will be to understand how implementation factors influence the optimal dose of our intervention. This evaluation may highlight which intervention components (or active ingredients) resulted in a change in behavior or other outcome result and potentially why (barriers/facilitators of change from an implementation standpoint).

Analyses for the Annie-texting pilot: Phase 1: these qualitative and interview data will be used to inform

consent and procedure development for Phase 2. No formal analytic methods will be used. Phase 2: feasibility will be assessed by looking at response rates through the Annie dashboard. At the end of phase 2, semi-structured interviews will take place among the participants regarding their opinions, barriers, and thoughts for improvement of the Annie texting system as tool to assist in pain management.

14. Provisions for Managing Adverse Reactions

We do not anticipate any adverse reactions as this study only involves interviews; hence, there is minimal risk of physical injury.

As part of the Annie texting pilot, we will develop orientation materials introducing the VA Annie texting system, which includes statements regarding safety and who to contact for questions or concerns. The Annie dashboard will be monitored twice/ week by the MOTIVATE research team for any concerning texts that may prompt a phone call for escalating symptoms. Similarly, if a subject persistently does not respond to any of the Annie text prompts, the research team will call the Veteran for a check-in and to trouble shoot any issues with technology.

15. Risk/Benefit Assessment

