The research involves a telephone-based program by a health coach over 10-20 weeks followed by an interview and in some, the Annie texting pilot; hence, there is minimal risk of physical injury. Participants will be asked to be more physically active and track their steps with a pedometer. As they become more active there is a risk of fall and injury. However, the health coach will focus on safely increasing walking and fall prevention strategies. The amount of activity we are asking participants to do is considered standard of practice and not strenuous activity that could result in injury. Another possible risk to patients is loss of time and potential breach of confidentiality. Risks include participant burden and resulting fatigue. There is no economic or legal risk in this study. To prevent or minimize any potential risks, patients may stop the interview at any point during this study if they feel any distress.

Discussing pain or psycho-social factors including comorbid depression may result in further psychological distress. There is no economic or legal risk in this study. To prevent or minimize any potential risks, the participant may stop the health coaching, assessments, or interview process at any time.

Since we will be recruiting older Veterans with comorbid depression, we have a plan in place should a Veteran be found to have worsening mental health conditions(s). If the Veteran develops worsening depressive symptoms during this study, the PCP will be notified to make appropriate follow-up or evaluation with Mental Health. In the case of suicidality endorsed over the telephone, as standard measures at the VA, we will provide the VA suicide hotline, warm transfer to mental health specialist, follow up with mental health services, and communication with the PCP. If the Veteran endorses suicidal or homicidal ideation during an in-person interview, the Veteran will be escorted to the Emergency Department for in-person psychiatric evaluation. The PI will be immediately notified of any de-escalation of mental health conditions.

All risks will be discussed in the consent form.

What is the overall risk classification for the research: minimal

Describe procedures that will be utilized to prevent/minimize any potential risks or discomfort? The subject will be told that they can stop participating in this study at any time if he or she becomes uncomfortable with Version 3.7, Updated 3/9/2021

the questions being asked.

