The other potential risk is a breach in confidentiality. All electronic data will be stored within password protected data management programs, on password protected computers. No non-study personnel will have access to study data. All research staff will be trained in the appropriate safeguarding of confidential data and in the protection of human subjects. At the end of the study, after analyses are complete, all study data will be de-identified, and the identifying key will be destroyed per VA policies and regulations.

We anticipate that our procedures to minimize risk of confidentiality will be highly effective. In the unlikely event of loss of patient confidentiality, we will have a procedure in place for responding in timely and appropriate manner. The study participant who experiences loss of confidentiality will be informed by the Principal Investigators ([name]) in writing and by phone of the loss of confidentiality. VA clinical leadership, the IRB and participant will be informed in the case of such an event.

16. Data Safety Monitoring

Does this study require a Data Safety Monitoring Plan (DSMP)? NO

Does this study have a Data Safety Monitoring Board (DSMB)? NO

17. Process for Obtaining Informed Consent and Protecting Patient Privacy

This study will be approved by the VA North Texas Health Care System Institutional Review Board (IRB). We will ask the IRB for a Waiver of HIPAA Authorization to identify Veterans who are eligible to be approached with requests to participate in the study. Such a waiver is justified because: minimal risk is anticipated; the waiver will not adversely affect the rights and welfare of subjects; and this aspect of the project cannot be practically conducted without waiver.

The study sample will be identified and enrolled using a multi-step screening process, very similar to successful processes that Drs. [name] and [name] use within the VA system. Through use of a HIPPA waiver, a list of Veterans 65 years old or older, with an ICD –10 code for back pain on the problem list in the last two years, will be generated from the VA corporate data warehouse. Eligible participants will have had at least one visit for cLBP in the last year.

We will obtain HIPAA-waiver for screening purposes and will employ *three separate recruitment techniques* that have been effective in earlier stages of this study (see sections 8 and 12).

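### Section 14 describes an interview-only study, Section 15 names a fall and injury risk, and the protocol gives no procedure to ascertain or compare falls and injuries by arm

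*Combined protocol and SAP*

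**What the plan says.** Section 14 (Provisions for Managing Adverse Reactions) gives as its premise: "We do not anticipate any adverse reactions as this study only involves interviews". It concludes that the risk of physical injury is minimal. The only monitoring it then describes is for the Annie texting subset.

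Section 15 (Risk/Benefit Assessment) describes a coached telephone program and states: "Participants will be asked to be more physically active and track their steps with a pedometer". The next sentence reads: "As they become more active there is a risk of fall and injury". As mitigation, "the health coach will focus on safely increasing walking and fall prevention strategies". The same paragraph then describes the activity as standard practice and "not strenuous activity that could result in injury". Section 15 also sets out responses to worsening depression and to suicidality.

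Section 16 answers: "Does this study require a Data Safety Monitoring Plan (DSMP)? NO". It also answers no to a monitoring board.

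Section 13 lists the study variables. They include RMDQ, PHQ-9 and pain measures, plus hospitalizations and clinic visits abstracted from the record at baseline, 3 and 6 (unit not given). Of the abstracted items it says: "These are important health utilization outcomes that will be explored in future studies". No item covers falls, injuries or adverse events. The proposed analyses in Section 13 apply exact binomial intervals to recruitment, adherence, retention and drop-out, and plan no harms table.

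**The concern.** The section that should provide for adverse events rests on a description the rest of the protocol contradicts. Sections 11 and 12 set out coaching sessions, a pedometer and step-count tracking, so participation goes well beyond interviews.

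The practical gap is in ascertainment. If nobody is asked a standard question, a fall or minor injury that leads to no recorded visit reaches the data mainly when a participant happens to mention it. Intervention participants speak with staff much more often than waitlist participants, so the opportunity to mention it differs by arm for reasons unrelated to how often falls occur. An apparent excess in the intervention arm could then be an artefact of contact, and a real excess could not be told apart from one.

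The pilot is meant to inform a larger effectiveness and implementation trial (Section 13). Whether older adults with back pain can raise their activity without excess falls or injuries is a natural question for that decision, and the plan as written would leave little usable information on it.

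**Working it through.** The plan states no harm rate, fall rate or power figure, so there is none to reproduce. The check is a comparison of the text, a count of contacts and an illustration of precision.

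**1. The statements side by side.**
- Section 14: interviews only, no adverse reactions expected.
- Section 15, first statement: increased activity carries a risk of fall and injury.
- Section 15, second statement, same paragraph: the activity is not of a kind that could cause injury.

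The first two conflict, and so do the last two. The eligibility criteria in Section 8 also treat physical risk as real: they exclude severe balance impairment, and they name a fall among the recent events that could make activity unsafe.

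**2. What existing data would capture.**
- Hospitalizations and clinic visits: events leading to recorded care, labelled as utilization. A fall without a recorded visit is missed.
- PHQ-9 and the suicidality procedure: mood only.
- RMDQ and pain measures: worsening function or pain, but not the event behind it.
- Patient Global Impression of Change: pain only, and its lowest category merges no change with worsening.
- Semi-structured interviews (Section 11): about 10 to 15 purposively chosen people, including coaches and providers.

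None of these asks every participant about falls or injuries.

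**3. Scheduled contacts up to the post-intervention call (Section 12).**
- Intervention: 8 modules + 3 check-ins = 11 coaching calls; adding the 5-week and 10-week assessments, 11 + 2 = 13.
- Waitlist: 2 assessments.
- Ratio: 13 / 2 = 6.5. Reminder calls before coaching sessions would widen it.
- If the 6- and 12-month assessments reach everyone, the totals are 13 + 2 = 15 against 2 + 2 = 4, before any coaching later offered to the waitlist arm.

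**4. Precision at the planned size (25 per arm, Section 9).** With zero events, the exact two-sided 95% upper limit is 1 − 0.025^(1/n).
- n = 25: 1 − 0.025^(1/25) = 13.7%.
- n = 50: 1 − 0.025^(1/50) = 7.1%.

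**5. Would events be seen at all?** The documents give no fall rate, so a range is assumed. The chance of at least one event in an arm of 25 is 1 − (1 − p)^25.

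| Assumed per-person rate p | Chance of at least one event |
|---|---|
| 2% | 39.7% |
| 5% | 72.3% |
| 10% | 92.8% |
| 20% | 99.6% |
| 30% | above 99.9% |

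From about 5% upward, events are more likely than not in each arm, so how they are counted matters.

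**The case against.** The strongest reply is that this is a small, minimal-risk feasibility pilot with reasonable safeguards. People with severe balance impairment or a recent illness that makes activity unsafe are excluded, coaches cover fall prevention, and both sections conclude that the risk of physical injury is minimal. These safeguards stand. They reduce risk but do not record events.

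A reader might infer that no harms are collected in either arm. The documents do not support that. Hospitalizations, clinic visits, PHQ-9, RMDQ and pain are collected without restriction by arm, and outcome calls go to all participants. Nor is it certain that the abstracted data will go unused here: they sit in the secondary outcomes list, and Section 13 plans to compare secondary outcomes between groups. The sentence deferring them to later studies leaves their role in this trial unclear.

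A reader might also infer that the Section 14 premise caused the omission. No section says so. The gap is shown by the absence of any procedure, not by the contradiction.

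Two further points stand. The unequal reporting is a foreseeable bias rather than a demonstrated one, because the plan proposes no comparison of falls. And the 13.7% limit is a consequence of sample size that applies equally after the fix, so it does not measure the defect.

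Finally, the assessment forms, manuals, activity instructions and consent form were not available. A fall or injury question in one of them cannot be excluded.

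**Conclusion.** The point holds, limited to the protocol text. Section 14 is untrue of this trial and conflicts with Section 15, which also conflicts with itself. No procedure is given to ascertain, record or compare falls, injuries or other physical adverse events by arm. Reports outside recorded care would be mainly volunteered, with about 13 scheduled contacts against 2 up to the post-intervention call. The contact count assumes that the sessions and assessments in Section 12 take place as scheduled.

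The change is worth making, because it alters what the pilot can report. It is tempting to go further and expect that, once amended, the pilot would establish whether the activity component is safe. At 25 per arm it would not: zero events would still be compatible with a true rate of up to 13.7%. What improves is that both arms are asked the same question at the same times.

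**What to change.** 1. Reconcile the Section 14 sentence with the two Section 15 statements. Which description of risk is right, and how events are managed clinically, is for the investigators to settle across the two sections.
2. Add one identical scripted item to each existing post-baseline assessment call in both arms, asking about falls, injuries, and emergency visits or hospitalizations since the last call. Word it without reference to the coaching program, since Section 5 has the assessor blinded.
3. Tabulate participants with events by arm, with exact 95% confidence intervals, alongside the abstracted hospitalizations, and label the table descriptive. Show the period up to the post-intervention call separately, because Section 5 later offers the intervention to the waitlist arm.
4. State in Section 13 whether the abstracted hospitalizations and visits are reported in this trial. If an attachment already contains a fall or injury question, cite it there.

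The cost is about a minute per call. With 4 post-baseline calls and 50 participants, that is at most 4 × 50 = 200 minutes over the study, plus one REDCap form, one table and a short amendment. Staff other than the coach already call both arms, exact binomial intervals are already planned, and the sample size does not change.

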The **third** recruitment strategy involves referral directly from a provider. [name] will provide a flyer to be posted in PRIME, ambulatory care, Rheumatology or PM&R clinics (see attached to this IRB protocol submission) outlining the eligibility criteria and brief synopsis of the study. If the Veteran is interested in learning more and participating in this study, he or she may call [name] or the study team at the number provider on the flyer, or, with the HIPAA waiver, the provider may notify [name] to call the Veteran (as additional cosigner on the clinic note). When/if [name] or her research team speaks with the Veteran (preferably in person but may be over the telephone if more convenient for the Veteran), we will describe the study, risks and potential benefits and obtain consent, also for audio-recording. The eligibility criteria will be assessed and confirmed over the phone or in person (whichever more convenient for Veteran) via self-report and review of CPRS data.

The inclusion and exclusion criteria (listed in detail in section 8) that will be assessed via the telephone or in person depending on recruitment method with a combination of self-reported measures, survey, and by review

of electronic medical record data. Veterans receiving mental health services at the time of the study recruitment will not be excluded. All mental health treatments and health service-use characteristics will be included in the study analyses as covariates. Verification of cLBP will be based on the self-report to questions listed in the eligibility screener (provided as supplemental document). Depression criteria will be based on participant self-report of clinically significant depressive symptoms according to the PHQ-9 (in person or via telephone screening). We will use the established cut-off score of ≥ 10 on the PHQ-9 to signify a clinically meaningful symptom burden. If the Veteran is not already enrolled in mental health clinic and scores ≥ 10 on PHQ-9, we will send the PCP a message in CPRS notifying him/her and suggesting further discussion about referral to mental health.

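### Section 15 tells staff to notify the PI of a *de-escalation* of mental health conditions, the reverse of the worsening the paragraph is about

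*Combined protocol and SAP*

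**What the plan says.** The mental health paragraph of Section 15 begins by saying that "we have a plan in place should a Veteran be found to have worsening mental health" conditions. It then gives three responses:

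- Worsening depression: "If the Veteran develops worsening depressive symptoms during this study, the PCP will be notified" so that follow-up or a mental health evaluation can be arranged.
- Suicidality disclosed by telephone: the VA hotline, a warm transfer, mental health follow-up and contact with the PCP.
- In person: "If the Veteran endorses suicidal or homicidal ideation during an in-person interview", staff take the Veteran to the Emergency Department.

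The paragraph closes with the sentence at issue: "The PI will be immediately notified of any de-escalation of mental health conditions".

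Two other places give the setting. Sections 8 and 12 require a PHQ-9 score of 10 or more for entry, a cut-off chosen "on the PHQ-9 to signify a clinically meaningful symptom burden". Section 16 answers both monitoring questions in the negative: "Does this study require a Data Safety Monitoring Plan (DSMP)? NO" and "Does this study have a Data Safety Monitoring Board (DSMB)? NO".

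**The concern.** The closing sentence is an instruction to staff about when the PI must hear of a change in a participant's mental health, and its trigger points the wrong way. Every Veteran in the trial is enrolled with clinically meaningful depressive symptoms, and the assessments and coaching calls are made by research staff and health coaches. With no DSMP and no DSMB, prompt notice to the PI is one of the few oversight steps written down. As worded, the protocol does not require immediate PI notice of deterioration, and adherence to the intended rule cannot be checked against the text.

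**Working it through.** No formula or planned figure is involved, so the check is textual. It asks two things.

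**1. Is the word reversed?** Set the parts of the Section 15 paragraph side by side.

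| Part of the paragraph | Direction of change | Who is told or what is done |
|---|---|---|
| Opening sentence | Worsening | Announces a plan |
| Depressive symptoms | Worsening | PCP |
| Suicidality by telephone | Deterioration | Hotline, warm transfer, mental health follow-up, PCP |
| Suicidal or homicidal ideation in person | Deterioration | Emergency Department |
| Closing sentence | *De-escalation*, i.e. improvement | PI, immediately |

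Only the last row runs the other way. Section 14, immediately before, uses *escalating* of symptoms to mean getting worse (the Annie dashboard check). By the protocol's own usage, then, *de-escalation* is the opposite of what the paragraph needs.

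**2. Does another sentence state the rule correctly?** Sentences using a form of *notify*, by section: Section 8, 1; Section 12, 3; Section 15, 2; Section 17, 3; Section 18, 1. Total: 1 + 3 + 2 + 3 + 1 = 10. By content:

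| Content | Count | Where |
|---|---|---|
| Provider refers a Veteran to the study team | 3 | Sections 8, 12, 17 |
| Enrolment notice to the PCP | 4 | Sections 12, 17 (twice), 18 |
| Depression notice to the PCP | 2 | Section 12 (screening), Section 15 (during the study) |
| Mental health notice to the PI | 1 | Section 15, worded *de-escalation* |

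3 + 4 + 2 + 1 = 10. The single PI notice is the reversed one, so none of the ten states PI notice of worsening in correct words.

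A keyword count can miss text that uses other words, so three further places were read:

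- **Section 12, suicidal ideation protocol.** It is written for potential participants, and its referral step applies to the screening process. The recipient's name is removed from the public copy, so it cannot be shown to be the PI. It covers suicidal ideation, not worsening depression.
- **Section 14, Annie dashboard.** The research team checks it twice a week, for the texting pilot only. The PI is not named.
- **Section 15, suicidality by telephone.** This requires contact with the PCP, a second PCP route in the same paragraph. The PI is not named.

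None of the three supplies the missing rule for enrolled Veterans.

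**The case against.** The strongest reply is that this is a copy-edit. Nobody would plausibly read the sentence as an order to call the PI when a Veteran improves; the clinical responses stand without it; and the study is classed as minimal risk. That is right about the consequence, and it is why the point is rated minor. It does not make the sentence correct: this is an operative safety instruction, and followed literally it triggers the wrong notice.

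A second reply is that the count of ten makes a single slip look like a rate, since nine of those sentences had other purposes. That is fair if the count is read as a size. Its only use here is to support the statement that no other sentence gives the rule correctly. The size of the problem is one sentence.

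A third reply is that swapping in *escalation* or *worsening* would be enough, and that naming suicidal or homicidal ideation adds a trigger. The shorter change would indeed cure the reversal. The longer phrase names only events the paragraph already covers, so it makes the evident intent explicit at no cost.

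Finally, the absence of a DSMP and DSMB has no bearing on whether the word is wrong. That is true; it bears only on why the sentence is worth correcting.

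**Conclusion.** The concern holds, at minor severity and with high confidence. One sentence in Section 15 states the reverse of what its paragraph requires, and it is the only mental health notice to the PI stated for the period after enrolment. There is no numerical effect: no estimate, feasibility outcome or analysis changes, and the clinical responses for a deteriorating Veteran remain in force. The conclusion takes *de-escalation* in its ordinary sense of lessening. It also relies on the Section 12 referral being limited to screening, as worded; because the recipient's name is removed, the documents cannot settle whether that person is the PI.

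**What to change.** In the last sentence of the mental health paragraph of Section 15, replace the *de-escalation* phrase so that the PI is immediately notified of *any worsening of a mental health condition, including any suicidal or homicidal ideation*. Nothing else in the section needs to change. The cost is one phrase in the next amendment, with no extra staff, visits or data collection and no change to the clinical responses.
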